11.2 Severity of Adverse Events

Investigators should assess the severity/intensity of any AE as follows:

Mild: The subject is aware of the event or symptom, but the event or symptom is easily

tolerated.

Moderate: The subject experiences sufficient discomfort to interfere with or reduce his or

her usual level of activity.

Severe: Significant impairment of functioning: the subject is unable to carry out usual

activities.

11.3 Causality Assessment

Investigators must assess the causal relationship between AEs and study drug (including any other non-medicinal product, radiation therapy, etc.) considering temporal relationship between the AE onset and study drug administration, safety profile of study drug (known ARs), the patient's condition (medical history, underlying disease), concomitant medication, and study procedures.

Related: Suspected to be reasonably related to any study medication.

Not related: Not suspected to be reasonably related to any study medication. A reasonable alternative explanation must be provided.

11.4 Recording of Adverse Events

The recording period for AEs begins, when the subject is initially included in the study (date of signature of first informed consent) and continues at least end of the mandatory safety-follow-up period at last study visit. However, as enrollment may take place from the time of cladribine prescription up until the second treatment week, in the first treatment year, any ADRs assessed as related to cladribine by the Investigator after the first dose of cladribine but before signature of Informed Consent must be recorded in the eCRF as well.

All adverse events, as specified above, occurring during the study, must be documented by the Investigator in the eCRF, including its description, seriousness, severity (grading), duration (onset

and resolution dates), causal relationship, any other potential causal factors, actions taken with the study drug (e.g. dose reduction, withdrawal), required treatment and outcome of the AE.

Note - Event term 'Death', 'Disability' and 'Hospitalization'

Death, disability, and hospitalization are considered outcomes in the context of safety reporting and not usually considered ARs/AEs. Therefore the primary cause of death, disability or hospitalization should be recorded and reported as an SAE/AR, and the outcome should be recorded in a separate data field. However, a term for the outcome will be selected if it is the only information reported or provides significant clinical information.

If death occurs, the primary cause of death or event leading to death should be recorded and reported as an SAE. "Fatal" will be recorded as the OUTCOME of this respective event and not be as separate event. Only, if no cause of death can be reported (for example, sudden death, unexplained death), the death per se might then be reported as an SAE.

Reports of Special Situations (see definition) are also to be recorded in the CRF following the AE procedure, even if occurring without AE.

Pregnancy and Breastfeeding. Pregnancy or breastfeeding must be recorded in the CRF and additionally be reported to the Sponsor immediately (within 24 hours of awareness) by using separate paper data collection forms for pregnancy, independent if an AE was reported or not. The outcome of the pregnancy should be followed up and reported to the Sponsor until delivery.

Women who become pregnant under therapy with Cladribine tablets should discontinue treatment.

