9.2.2 Definition of Study Cohorts and Description of Treatments

This is a single cohort study enrolling all patients that switch to Cladribine tablets from first-line DMDs, according to the decision of the treating physician. Patients should have been under treatment with first-line DMDs for at least one year prior to switching (see Section 9.2.1) and should have been prescribed to Cladribine tablets prior to enrollment (baseline visit). Enrollment may take place from the time of cladribine prescription up until the second treatment week, in the first treatment year.

All eligible patients are treated with Cladribine tablets in routine clinical practice. Patients will receive Cladribine as per the SmPC and the discretion of their treating physician. According to the SmPC, each treatment course consists of 2 treatment weeks, one at the beginning of the first month and one at the beginning of the second month of the respective treatment year. Each treatment week consists of 4 or 5 days on which a patient receives 10 mg or 20 mg (one or two tablets) as a single daily dose, depending on body weight. If necessary, the treatment course in Year 2 can be delayed for up to 6 months to allow for recovery of lymphocytes (at least 800 cells/mm³). If this recovery takes more than 6 months, the patient should not receive Cladribine tablets anymore. In patients where cladribine tablet treatment was delayed, follow-up will remain 2 years after enrollment and will not be extended by the period by which treatment was delayed.

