9.7 Data Analysis

Statistical programming and analyses will be performed using SAS 9.4 (or higher). Detailed methodology for summary and statistical analyses of data collected in this study will be documented in a statistical analysis plan (SAP), which will be finalized prior to database lock and will be included in the clinical study report for this protocol. The final SAP will take into account any amendment to the protocol.

All analyses will be performed on patients who received at least one dose of Cladribine tablets following enrollment in the study.

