9.9 Limitations of the Research Methods

This study is open label and observational, and therefore has inherent limitations in terms of susceptibility to bias, confounding and restricting the ability to define causality. There is limited control over patient assessment as patient monitoring and diagnostics are per standard of care; no additional clinical monitoring is generally conducted. Patient specific methodological challenges such as potential biases from patient selection, loss of patients through study attrition, and overall patient recall are also other limitations. However, observational study strengths include that they reflect daily clinical practice more closely than randomized controlled trials, both in terms of the heterogeneous patient populations that are included, and the medical interventions that they receive. Real-life observational data is essential to assess and improve clinical practice worldwide and complement randomized controlled trials by providing clinically-relevant, real-world data and provide considerable health economic information.

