## 13 Study Treatment: Adherence and Exposure

The following analyses will be performed based on the FAS. All dosing calculations and summaries will be based on "Cladribine Administration" CRFs pages.

Cladribine is administered in the first 2 weeks of each the 2 years of treatment planned. Therefore, it is not accurate to report treatment duration based on the date of last cladribine administration. Cladribine treatment exposure will then be summarized as number and percentage of patients who completed the treatment overall and for each of the 4 treatment courses (Year 1: Week 1, Year 1: Week 2, Year 2: Week 1 and Year 2: Week 2). Overall and for each treatment course, the number and percentage of patients with dose delays or dose changes will be reported, including the associated reasons. Number and percentage of patients who permanently discontinued the treatment and associated reasons for discontinuation will also be reported.

Cladribine utilization and adherence will be summarized for each treatment course (Year 1: Week 1, Year 1: Week 2, Year 2: Week 1 and Year 2: Week 2) and overall. For each treatment course, the following information will be presented:

- Dose, calculated as Number of tablets taken × 10/Weight (kg) at time of prescription
- Number of tablets prescribed
- Number of tablets taken
- Adherence to treatment, calculated as 100 × Taken tablets/Prescribed tablets. Adherence will also be presented under the following categories
  - <60%
  - 0 [60%-80%]
  - 0 [80%-90%]
  - o [90%-100%]

For the overall summary, the cumulative dose will be presented instead of dose. The cumulative dose will be calculated as the sum of all doses from all available treatment courses prior to treatment discontinuation or end of the 2 years treatment period.

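### Consent may follow the first dose by up to about a month, so patients who stop in Week 1 and never consent are missed; early discontinuation and Year 1 completion are likely to look too good, by an unmeasured amount

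*Protocol*

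**What the plan says.** Protocol Section 9.2.2 sets the window: "Enrollment may take place from the time of cladribine prescription up until the second treatment week, in the first treatment year". It places the two treatment weeks of a course "one at the beginning of the first month and one at the beginning of the second month" of the treatment year. SAP Section 9.1 expects some patients to enrol after dosing, since it allows for baseline data collected retrospectively.

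Recording of adverse events starts at first consent (Protocol Section 11.4). That section makes an allowance for late consent, "as enrollment may take place from the time of cladribine prescription up until the second treatment week, in the first treatment year". The one exception for late consenters is "any ADRs assessed as related to cladribine by the Investigator after the first dose of cladribine but before signature of Informed Consent", which must also be entered in the eCRF.

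The analysis clock starts earlier, at first dose. That holds for Day 1 (SAP 9.2), the on-treatment period (9.7), treatment-emergent events (9.8.1) and length of follow-up (10.1). SAP Section 13 will report the "number and percentage of patients who completed the treatment overall and for each of the 4 treatment courses", with Year 1 Week 1 and Year 1 Week 2 as two of the four.

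The documents disagree on who is analysed. Protocol Section 9.7 states: "All analyses will be performed on patients who received at least one dose of Cladribine tablets following enrollment in the study". Protocol Section 9.7.1 and SAP Section 8.1 ask only for consent and at least one dose, with no condition on timing. SAP Section 10.2.2 gives absence of any dose as the only ground for exclusion.

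**The concern.** This is left truncation. Risk time starts at first dose, but a patient enters the data only by consenting, possibly weeks later. Someone who reacts to Week 1, gives up treatment and is never enrolled has no eCRF. The back-recording rule cannot reach that patient, because it applies only to people who later sign.

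Patients lost this way are more likely to be treatment failures than successes, so the expected error runs in the product's favour. The results exposed are Year 1 Week 1 and Week 2 completion, early permanent discontinuation, events leading to discontinuation and, less strongly, early drug reactions. All of these pool early and late consenters in one denominator. A reader of the report could not tell whether a low early-stop rate reflects tolerability or the timing of consent.

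**Working it through.** The plan states no figure to reproduce, so the check has two parts.

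**Does anything in the plan capture or measure the missing patients?**

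- Consecutive enrolment (Protocol 9.1.1) does not say when in the window a patient must be approached.
- The SAP Modification History records that the screening-log reference was removed as not feasible to collect, and the current SAP has none.
- Disposition (SAP 10.1) starts from a study-entry form and is broken down by country and site, not by consent timing. Consent must precede any study activity (Protocol 10.1), so a patient who never consents should have no form.
- Section 9.9 refers to "potential biases from patient selection" in general terms and does not mention this mechanism.

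The answer is no.

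**How large could the effect be?**

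The documents give none of the three inputs below, so all are assumptions shown over a range:

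- q = true share of starters who stop for good before Week 2
- f = share of starters approached only after that point
- s = share of late-approached stoppers who never enrol

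Enrolled stoppers are (1 − f)q + fq(1 − s) = q(1 − fs). All enrolled patients are 1 − fqs. Hence:

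observed stop rate = q(1 − fs) / (1 − fqs)

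For q = 3%, f = 50%:

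- s = 1: 0.03 × 0.50 / (1 − 0.015) = 0.0150 / 0.9850 = 1.52%
- s = 0.5: 0.03 × 0.75 / (1 − 0.0075) = 0.0225 / 0.9925 = 2.27%

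Observed rates for q = 3%, with the number of stoppers among the planned 242 patients in brackets (the true rate would give 242 × 0.03 = 7.3):

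| | f = 0 | f = 25% | f = 50% | f = 75% |
|---|---|---|---|---|
| s = 1 | 3.00% (7.3) | 2.27% (5.5) | 1.52% (3.7) | 0.77% (1.9) |
| s = 0.5 | 3.00% (7.3) | 2.63% (6.4) | 2.27% (5.5) | 1.90% (4.6) |

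The same calculation at other true rates, for f = 25%, 50% and 75%:

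| q | s = 1 | s = 0.5 |
|---|---|---|
| 1% | 0.75%, 0.50%, 0.25% | 0.88%, 0.75%, 0.63% |
| 5% | 3.80%, 2.56%, 1.30% | 4.40%, 3.80%, 3.18% |
| 10% | 7.69%, 5.26%, 2.70% | 8.86%, 7.69%, 6.49% |

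The relative understatement is close to f × s whatever the value of q. In absolute terms it stays under 4 points when q is 5% or less (largest case 5.00% − 1.30% = 3.70 points).

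**What Section 9.7 adds.** Under the Full Analysis Set wording, a patient who stopped in Week 1 and consents afterwards is counted, so s can be below 1. Read literally, Section 9.7 removes that patient, because no tablet is taken after enrolment. The s = 1 row then applies even if every such patient consents.

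**The case against.** A reader might infer that late enrollees can enter only if they got past Week 1. The documents do not support that. Eligibility (Protocol 9.2.1 and 9.2.2) requires a prior prescription and has no continuation criterion, and patients who stop cladribine stay in follow-up unless they switch to another disease-modifying drug (9.2.3, 9.2.5). An early stopper may consent within the window.

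A reader might also infer that the analysis rules make it impossible for a late enrollee to count as a Week 1 stopper. That rests on one sentence in Section 9.7. The tables in SAP Sections 13 and 15 run on the Full Analysis Set, which would include such a patient. What the documents show is a contradiction, not a settled exclusion.

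For reactions the case is weaker than for stopping. Related reactions before consent are recorded, so late enrollees do contribute early events; only reactions in people who never enrol are lost. The calculation covers stopping and shows no figure for reactions.

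Importance is also limited. Confirmatory testing is confined to the primary outcome (SAP 9), the safety objective is set at two years, and the adherence endpoint is tablets taken against tablets prescribed. The SAP states openly that enrolment may follow dosing, and consent dates will be listed.

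All of this stands and narrows the claim. None of it recovers or counts the patients who never consent.

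**Conclusion.** The mechanism holds and the plan neither corrects nor measures it. The expected direction is favourable whenever f and s are both above zero. It cannot be said from the documents that the figures are biased, or by how much: if all patients consent on or before first dose, which the protocol allows, the effect is nil. Under the assumed 3% early stopping with half of starters approached late, the reported rate would be 1.5% to 2.3%, or 3.7 to 5.5 patients of 242 instead of 7.3. These numbers rest wholly on assumed q, f and s. The effect is on early discontinuation and Year 1 completion first, and on early drug reactions less; no effect on the primary relapse-rate comparison is claimed. The mismatch between Protocol Section 9.7 and the Full Analysis Set is a definite inconsistency whatever the size of the bias.

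**What to change.** 1. Reconcile Protocol Section 9.7 with Protocol 9.7.1 and SAP 8.1 and 10.2.2, so that a consented patient with any cladribine dose is analysed.
2. In SAP Section 10.1, report the number who consented on or before first dose and the number who consented after it. Consent date is already listed there, and treatment dates are required eCRF fields (SAP 9.8).
3. In SAP Sections 13 and 15.1, show Year 1 Week 1/Week 2 completion, early permanent discontinuation, and treatment-emergent events and drug reactions with onset up to the end of Year 1 Week 2, by that split and beside the pooled result. Interpret early tolerability from the group that consented on or before first dose, which is free of this selection. Later-period results can stay pooled.
4. Keep the pre-consent reactions of late enrollees in their own column. Counting these patients at risk only from consent would discard the reactions that Section 11.4 deliberately collects, and has no clear meaning for completion of a week that ended before consent.
5. Name the mechanism in Protocol Section 9.9.

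The cost is some protocol and SAP wording and a few table columns, with no new data. Early-period estimates from the subset will rest on fewer patients and have wider intervals. If late consent proves rare, the count in step 2 lets the sponsor show that the problem is negligible.

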Patients will be enrolled consecutively at study sites in the participating countries. Each patient will be followed for the course of their standard Cladribine treatment (approximately 2 years according to clinical practice).

Figure 1 provides a schematic overview of the study design. Figure 2 provides an overview of the patient journey within the study. Enrolment may take place from the time of cladribine prescription up until the second treatment week, in the first treatment year.

[figure not shown]
[figure not shown]

Figure 1 - Schematic of Study Design³

³ Pts: patients: IFN: Interferon; DMF: Dymethyl fumarate; DMD: Disease Modifying Drug

* Interferon, Glatiramer Acetate, Teriflunomide, DMF

Figure 2 - Study Patient Journey

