#### 9.7 Definition of On-treatment Period

The on-treatment period is defined as the date of the first dose of study treatment to the date of the last contact. Due to the posology and long-term effects of Cladribine, a patient is on-treatment from the first dose received of Cladribine until the follow-up period ends.

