#### 9.8.1 TEAE classification

Rules presented in Table 1 will be used for classification of AEs as Treatment-Emergent Adverse Events (TEAEs). An AE is considered a TEAE if started on or after study treatment start date.

Table 1 TEAE Classification rules

Start date of AE		Start date of AE	TEAE classification
Day	Month	Year	
UNK	UNK	UNK	TEAE
UNK	UNK	< Treatment start (year)	Not TEAE
UNK	UNK	≥ Treatment start (year)	TEAE
UNK	UNK < Treatment start (month and year)		Not TEAE
UNK	≥ Treatment start (month and year)		TEAE
< Treatment start (complete date)		(complete date)	Not TEAE
≥ Treatment start (complete date)		(complete date)	TEAE

AE = Adverse event; TEAE = Treatment-emergent adverse event; UNK = Unknown

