## 15 Safety Analyses

Safety analyses will be done on the FAS.

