#### 15.1 Adverse Events

The TEAE are those events with onset dates occurring within the on-treatment periods as defined in Section 9.7.

The AEs related to study treatment are those events with relationship missing or "Related".

All analyses described in Section 15.1 will be based on TEAEs if not otherwise specified. The AE listings will include all AEs (whether treatment-emergent or not). AEs outside the on-treatment period will be flagged in the listings.

Unless otherwise specified, TEAEs will be summarized by number and percentage of patients with the TEAE in the category of interest, primary SOC and PT in decreasing frequency.

Each participant will be counted only once within each SOC or PT. If a participant experiences more than one AE within a SOC or PT for the same summary period, only the AE with the strongest relationship or the worst severity, as appropriate, will be included in the summaries of relationship and severity.

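### Until consent, only cladribine-related reactions must be recorded, but TEAEs count from first dose for everyone: a small, first-month tilt in the safety tables for patients dosed before consent

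*Protocol*

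**What the plan says.** Protocol 9.2.2 allows consent after dosing has begun: "Enrollment may take place from the time of cladribine prescription up until the second treatment week, in the first treatment year". The same section places the second treatment week at the start of month 2, with 4 or 5 dosing days.

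Protocol 11.4 opens the AE recording period on the date of first informed consent. It makes one explicit exception for earlier time: "any ADRs assessed as related to cladribine by the Investigator after the first dose of cladribine but before signature of Informed Consent" must also go into the eCRF.

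Protocol 11.5 makes all SAEs reportable whatever their relationship to the drug, and AESIs as well, but states no date from which this applies.

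The SAP uses a different starting point. In 9.7, "The on-treatment period is defined as the date of the first dose of study treatment to the date of the last contact". In 9.8.1, "An AE is considered a TEAE if started on or after study treatment start date". In 15.1, "The TEAE are those events with onset dates occurring within the on-treatment periods as defined in Section 9.7". SAP 15 adds that "Safety analyses will be done on the FAS", which includes patients who consented after their first dose. SAP 15.1.1 then tabulates TEAEs by seriousness, special interest and relationship.

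**The concern.** The recording window and the counting window do not start together for patients dosed before consent. In the interval between the two dates, a related reaction must be recorded, while an unrelated event is not clearly required to be. Each such patient still contributes to the TEAE tables as if observed in full from first dose. Any loss goes one way: incidence can only fall, and the related share can only rise.

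SAP 9.1 deals with late enrolment for baseline questionnaires and disability scores. No SAP rule does so for adverse events: nothing conditions a TEAE on consent, flags pre-consent onset or separates late enrollees. Safety at two years is a secondary objective, and the interim outputs in SAP 18.2 include the TEAE overview, serious TEAEs and TEAEs by relationship. A reader of those tables could not tell that part of the time was observed selectively.

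**Working it through.** The plan gives no adverse event rate, no safety precision target and no expected share of late enrollees, so there is no figure of its own to reproduce. The check compares the two windows and then sizes the gap under stated assumptions.

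**Length of the gap.** One month is 30.4375 days (SAP 9.4). Adding up to 5 dosing days gives 30.4375 + 5 = 35.4 days at most. Follow-up is 24 months from first dose (Protocol 9.2.3): 24 × 30.4375 = 730.5 days. The maximum gap is 35.4/730.5 = 4.85% of follow-up; a 14-day gap is 14/730.5 = 1.92%. Against 12 months, the follow-up that triggers the interim analyses, the maximum is 35.4/365.25 = 9.7%.

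**What can be lost.** This depends on two points that the protocol leaves open.
- *Scope.* Protocol 9.1.2.2 and 11.4 speak of adverse events in general. Protocol 9.3 and the abstract list only SAEs, AESIs and ADRs as safety variables.
- *Start date for SAEs and AESIs.* If the recording period in 11.4 governs 11.5, unrelated SAEs and AESIs before consent need not be recorded. If 11.5 stands alone, they must be.

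With broad scope and 11.4 governing, all unrelated events in the gap can be lost. With narrow scope and 11.4 governing, only unrelated SAEs and AESIs can. With narrow scope and 11.5 reaching back to first dose, nothing is lost.

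**Size.** Assumptions: N = 242 (Protocol 9.5), constant rates u (unrelated) and r (related) per patient-year, share f dosed before consent, gap g in years, observation time T in years. Unrelated events in the gap are all lost and related ones all kept.
- True incidence: 1 − exp[−(u + r)T]
- Observed incidence: (1 − f) × true + f × {1 − exp[−(u(T − g) + rT)]}
- Observed related share of events: rT / [u(T − fg) + rT]
- Unrelated events lost: N × f × g × u

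Worked case: f = 0.5, g = 35.4/365.25 = 0.0970, u = 1.0, r = 0.5.
- 24 months (T = 2): true 1 − exp(−3) = 95.0%; late enrollees 1 − exp(−2.903) = 94.5%; observed overall 94.8%. Related share: 1/2.951 = 33.9%, against 33.3%.
- First 35 days (T = g): true 13.5%, observed 9.1%. Related share: 50.0%, against 33.3%.
- Events lost: 242 × 0.5 × 0.0970 × 1.0 = 11.7.

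All cases, true → observed:

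| f, gap, u/r | 24-month incidence | 24-month related share | First-35-day incidence | First-35-day related share |
|---|---|---|---|---|
| 0.25, 14 d, 1.0/0.5 | 95.02 → 94.97% | 33.3 → 33.4% | 13.5 → 12.7% | 33.3 → 35.7% |
| 0.5, 35.4 d, 1.0/0.5 | 95.02 → 94.77% | 33.3 → 33.9% | 13.5 → 9.1% | 33.3 → 50.0% |
| 0.5, 35.4 d, 0.05/0.02 | 13.06 → 12.85% | 28.6 → 29.1% | 0.68 → 0.44% | 28.6 → 44.4% |
| 1.0, 35.4 d, 1.0/0.5 | 95.02 → 94.51% | 33.3 → 34.4% | 13.5 → 4.7% | 33.3 → 100% |
| 1.0, 35.4 d, 0.05/0.02 | 13.06 → 12.64% | 28.6 → 29.6% | 0.68 → 0.19% | 28.6 → 100% |

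The 0.05/0.02 rows stand for SAE-like rates; at f = 0.5 they lose 242 × 0.5 × 0.0970 × 0.05 = 0.6 unrelated events. With f = 0 every difference is zero. The related share here is counted by event; the SAP tables count patients by strongest relationship, so the share is an indicator and not a planned statistic.

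**The case against.** The best counter-argument is Protocol 11.5. It wants every SAE and AESI reported, related or not, and the sentence in 11.4 adds a duty without forbidding other entries. A reader might infer that unrelated SAEs and AESIs before consent are definitely left out. The documents do not say that. Equally, they do not say that 11.5 reaches back to first dose: the only recording period given is the one in 11.4, and an exception limited to related reactions would be odd if everything serious were already covered. What stands is an ambiguity that sites can resolve differently.

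A reader might also infer that the study will report materially wrong early safety rates. It plans no early-period table and no related-share statistic. The tables in SAP 15.1.1 cover the whole on-treatment period, where the shift is small. If only SAEs, AESIs and ADRs are collected, the related/unrelated split is selective throughout follow-up by design, and the window mismatch adds little to that.

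Early lymphopenia is a tempting example but a weak one. Protocol 7.2 names it as the most commonly reported adverse event in the phase III trial. Protocol 11.3 demands an alternative explanation before an event is called unrelated, and SAP 15.1 counts a missing relationship as related. It is unlikely to be filtered out.

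Finally, the exception in 11.4 is deliberate and gives its reason, safety is descriptive, and 35 days is the extreme. Before the second treatment week the gap includes no more than the first week of dosing. These points limit the size of the problem; they do not align the two windows.

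**Conclusion.** The mismatch is real and minor. For patients consented after first dose, the protocol explicitly requires only related ADRs for the pre-consent time, while the SAP counts TEAEs from first dose for the whole FAS. Unless 11.5 is meant to reach back and collection is limited to SAEs, AESIs and ADRs, incidence is slightly understated and the split leans slightly towards related.

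Over 24 months, incidence moves by about 0.2 points with half the patients at the longest gap, and by about 0.5 points or less with all of them there. The related share moves by about 1 point or less in every case run. The first month can be distorted much more, but it is not tabulated on its own. These sizes rest on assumed constant rates and an assumed share of late enrollees; they would be larger if unrelated events clustered just after dosing. The primary endpoint is untouched.

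**What to change.** **Protocol 11.4.** State that SAEs and AESIs from first dose are recorded at the baseline visit from the medical record, regardless of causality. This also settles the start date for 11.5.

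**SAP 15.1.** Report the number of patients dosed before consent and the length of the gap, and present the TEAE overview separately for patients consented before and after first dose. An alternative is to count TEAEs from the later of first dose and consent. Pre-consent ADRs must then be tabulated separately, or the events that 11.4 deliberately captures would drop out.

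**Cost.** The recording change amends a protocol rule and needs a short retrospective record check for late enrollees. The SAP change is one extra table from dates already held: consent date is in the disposition listing (SAP 10.1), and treatment dates are required to be complete (SAP 9.8). If non-serious unrelated events are in scope, the recording change does not recover them, but the split table exposes the difference.
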